9.0 STATISTICAL CONSIDERATIONS

9.1 Sample Size and Study Duration

The proposed randomized Phase 2 study will require enrollment of 90 eligible patients, 45 assigned to each regimen. Enrollment may proceed up to 95 patients to allow up to 5% potentially ineligible patients.

Expected accrual for this study would be similar to the accrual rate of 42 patients/year observed on the ANBL1221 expansion cohort at non-Australian and New Zealand sites as the patient population and eligibility are very similar. We anticipate that given the positive results of ANBL1221 and the reality that this backbone has become widely used for first relapse, there should be similar accrual rates for this trial. Assuming this rate, the trial would take about 2.3 years to complete accrual of up to 95 patients. The study will require an additional 12 months for completion of therapy and toxicity evaluation for a total study duration of approximately 3.3 years.

The sample size may be increased if accrual is fast: specifically, if 30 months after the study commencement the average accrual rate over the previous 3 months is above an annual rate of 41 patients per year, then the study may be amended (blindly to the interim outcome data) and accrual increased to 148 eligible patients. In this case, enrollment may proceed up to 155 patients to allow up to 5% potentially ineligible patients. Assuming an accrual rate of 42 patients/year (this rate would be amended if needed based on observed accrual rate), the trial would take about 3.7 years to complete accrual and a total study duration of ~4.7 years. The amendment would be submitted after the 30-month time point so that the study will not need to be closed to accrual as a result of the increase in the target accrual.

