9.3.4 Assessment of Study Objectives

The primary study aim ([1.1.1](#)) will be assessed by a one-sided continuity-corrected test of proportions with pooled variance to compare the response rates after 6 cycles in the two regimens, and the futility and efficacy monitoring rules ([Section 9.3.3](#)). The response rate by the end of 6 cycles will be calculated on each regimen, including placement of a 95% confidence interval. If a patient is a responder and later has PD or goes off protocol therapy, then the patient will be counted as a responder. If the response rate on Regimen B is significantly better, then it will be considered a therapeutic regimen worthy of further testing in patients with newly-diagnosed high-risk neuroblastoma. In addition, the response rate by the end of 6 cycles (based on confirmed responses) will also be calculated for each regimen, with responders defined as patients who achieve a confirmed minor response or better per the revised INRC⁶⁸ as their best overall response by the end of 6 cycles as determined by central review.

To address secondary objective [1.2.1](#), Kaplan-Meier curves of PFS and OS will be generated by regimen and compared using log-rank tests. PFS and OS will also be evaluated separately in the cohorts of patients enrolled prior to and post-Amendment 4 given the reduction in maximum cycles of therapy from 17 to 6 cycles.

To assess secondary aim [1.2.2](#), toxicities (Grade ≥ 3) experienced on Regimen B will be descriptively summarized.

Exploratory aim [1.3.1](#) will be assessed by exploring the relationship between response (responder vs. non-responder) after 6 cycles on Regimen B with serum cytokine levels (IL1, IL6, TNF-alpha, IFN-gamma, etc.), tumor resident immune cells (NK cells, TAMS, TILS), and critical immune cell suppressing proteins (B7H3, PDL-1) using Fisher's exact test for categorical and Wilcoxon rank-sum test for continuous factors.

To address exploratory objective [1.3.2](#), GD2 levels in tumor cells from bone marrow samples will be correlated with response (responder vs. non-responder) after 6 cycles using Fisher's exact test for categorical and the Wilcoxon rank-sum test for continuous factors.

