To assess exploratory aim [1.3.3](#), the occurrence of pain on each regimen as reported by patient report and opiate use will be descriptively summarized. Descriptive and summary statistics will be used to describe the scores from the Faces Pain Scale-Revised during the dinutuximab infusion and on Day 1 with irinotecan and temozolomide alone for each arm separately. Confidence intervals will be constructed for the mean and frequency estimates. The Day 1 patient reported outcome data are expected to be similar between the 2 regimens, while differences during or after completion of treatment may be observed.

9.4 **Evaluability for Response**

All eligible patients will be considered evaluable for response.

9.5 **Evaluability for Toxicity**

All eligible patients will be evaluable for toxicity from the time of their first treatment with eflornithine, irinotecan, temozolomide, or dinutuximab.

The study committee will review ototoxicity data closely during monthly committee meetings. If a difference in the incidence of hearing loss of $>15\%$ in eligible patients treated on the interrupted schedule enacted with Amendment 2A is detected among patients on the DFMO-containing Regimen B as compared to Regimen A, the study committee will notify the DSMC and CTEP and discuss potentially suspending accrual and further modifying the DFMO dose and/or schedule. In this context, hearing loss is defined as “an increase of 15dB or more from baseline in hearing threshold at two contiguous frequencies between 500-3000Hz” as this is the criterion for which DFMO is held for hearing loss.

9.6 **Gender and Minority Accrual Estimates**

The gender and minority distribution of the study population is expected to be:

DOMESTIC PLANNED ENROLLMENT REPORT								
Racial Categories	Ethnic Categories						Total	
	Not Hispanic or Latino		Hispanic or Latino					
	Female	Male	Female	Male				

American Indian/ Alaska Native	0	0	0	0	0
Asian	0	3	0	0	3
Native Hawaiian or Other Pacific Islander	0	0	0	0	0
Black or African American	8	5	0	0	13
White	18	29	5	10	62
More Than One Race	0	0	0	0	0
Total	26	37	5	10	78

INTERNATIONAL (including Canadian participants) PLANNED ENROLLMENT REPORT						
Racial Categories	Ethnic Categories				Total	
	Not Hispanic or Latino		Hispanic or Latino			
	Female	Male	Female	Male		
American Indian/ Alaska Native	0	0	0	0	0	
Asian	0	2	0	0	2	
Native Hawaiian or Other Pacific Islander	1	1	0	0	2	
Black or African American	0	0	0	0	0	
White	4	7	2	0	13	

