10.2.1 Definitions

10.2.1.1 Evaluable for toxicity: All eligible patients will be evaluable for toxicity from the time of their first treatment with eflornithine, or irinotecan, temozolomide or dinutuximab.

10.2.1.2 Evaluable for response: All eligible patients will be considered evaluable for response. These patients will have their response classified according to the definitions stated below.

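### The planned toxicity summary and the hearing-loss trigger count only eligible patients, so a patient who was dosed and later ruled ineligible is left out of both

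*Combined protocol and SAP*

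**What the plan says.** Section 9.5 defines who counts for toxicity: "All eligible patients will be evaluable for toxicity from the time of their first treatment with eflornithine, irinotecan, temozolomide, or dinutuximab". Section 10.2.1.1 gives the same definition: "Evaluable for toxicity: All eligible patients will be evaluable for toxicity from the time of their first treatment with eflornithine, or irinotecan, temozolomide or dinutuximab".

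The second paragraph of 9.5 sets the hearing-loss trigger. The study committee notifies the DSMC and CTEP if the difference in incidence between Regimen B and Regimen A is more than 15%, and the comparison is made "in eligible patients treated on the interrupted schedule enacted with Amendment 2A is detected among patients on the DFMO-containing Regimen B".

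For secondary aim 1.2.2, Section 9.3.4 says that toxicities of Grade 3 or higher "experienced on Regimen B will be descriptively summarized". It names no population of its own, so the definition in 9.5 governs.

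Section 9.1 expects some enrolled patients to be ineligible. The trial "will require enrollment of 90 eligible patients, 45 assigned to each regimen", and "Enrollment may proceed up to 95 patients to allow up to 5% potentially ineligible patients". If the sample size is raised to 148 eligible patients, "In this case, enrollment may proceed up to 155 patients to allow up to 5% potentially ineligible patients".

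**The concern.** Restricting a response rate to eligible patients is a coherent choice, because it fixes the population to which the efficacy question applies. Eligibility has no bearing on whether a harm occurred after dosing. Once a patient has received the regimen, what follows is evidence about its toxicity.

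Patients who are treated but ineligible are foreseeable under this protocol. Section 3.2 says that the criteria are read literally and cannot be waived, and that source records are checked at audit, so ineligibility can come to light after treatment. Section 3.1.5 names one group who have been treated by definition: those who start protocol therapy before enrollment.

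Two outputs are at stake: the toxicity summary that answers aim 1.2.2, and the only numerical between-arm toxicity threshold in the plan. That threshold matters here because, according to Section 2.5, four of the first eight Regimen B patients with ototoxicity data had Grade 3 hearing loss, which led to the interrupted DFMO schedule. It counts only patients on that schedule, so its denominators are small, especially early on.

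**Working it through.** **1. The plan's own figures.** Inputs from Section 9.3.1.1: 40% vs 60%, one-sided type I error 20%, power 80%, continuity-corrected test with pooled variance. The uncorrected size per arm is (0.8416·√(2·0.5·0.5) + 0.8416·√(0.4·0.6 + 0.6·0.4))² / 0.20² = 34.7. With the continuity correction it is (34.7/4)·(1 + √(1 + 4/(34.7·0.20)))² = 44.1, rounded up to 45. That is 90 eligible patients, as stated. Allowing 5% ineligible gives 90/0.95 = 94.7, rounded up to 95, also as stated. For the expansion, 148/0.95 = 155.8 against a stated cap of 155, which is close enough. No stated figure is wrong on this point; these figures only size the excluded group.

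**2. Size of the excluded group.**
- Base design: 95 − 90 = 5, and 5/95 = 5.3%.
- Expanded design: 155 − 148 = 7, and 7/155 = 4.5%.

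Both are ceilings. They are enrollment allowances, and some ineligible patients may never be dosed. An even split of 5 would put 2 or 3 on each regimen; that split is an assumption.

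**3. Sensitivity of the hearing-loss trigger.** The trigger is read as B minus A of more than 15 percentage points. The counts are illustrative, because the documents give none for the interrupted schedule.

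| Eligible patients only | Difference | Treated ineligible patients added | Difference |
|---|---|---|---|
| B 3/20, A 0/20 | 15.0, does not fire | one on B, with hearing loss: B 4/21 | 19.0, fires |
| B 4/30, A 0/30 | 13.3, does not fire | one on B, with hearing loss: B 5/31 | 16.1, fires |
| B 6/45, A 0/45 | 13.3, does not fire | one on B, with hearing loss: B 7/46 | 15.2, fires |
| B 4/25, A 0/25 | 16.0, fires | two on B, without hearing loss: B 4/27 | 14.8, does not fire |
| B 7/45, A 0/45 | 15.6, fires | one on A, with hearing loss: A 1/46 | 13.4, does not fire |

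In four of these five cases a single patient changes the outcome. The direction depends on the arm and on whether that patient had the event.

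**4. The toxicity summary.** Suppose no Grade 5 event occurs in 45 eligible Regimen B patients. The exact one-sided 95% upper limit is 1 − 0.05^(1/45) = 6.4%. Suppose one such event occurs in a treated but ineligible Regimen B patient, and 2 or 3 ineligible patients are added. The upper limit p solves (1 − p)^n + n·p·(1 − p)^(n−1) = 0.05, which gives 9.7% for 1/47 and 9.5% for 1/48. The point estimate moves from 0% to 2.1%.

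For a commoner event, 4/45 (8.9%) could become anything from 4/48 (8.3%, none of three added patients has the event) to 7/48 (14.6%, all three do).

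**5. Chance that an event is lost.** With 3 excluded Regimen B patients and a true event rate p, the chance of at least one event among them is 1 − (1 − p)³. This is 14% at p = 5%, 39% at 15%, 58% at 25% and 88% at 50%. The documents give no rate for such patients, so this range is an assumption.

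**The case against.** The strongest reply is that safety oversight does not depend on the 9.5 definition. Routine reporting in 11.12 takes every Grade 3 or higher adverse event. Serious events must be reported whether or not related (11.9), and deaths within 30 days of the last dose are reported regardless of attribution (11.4.3). DSMC review under 12.2 covers serious events on the trial as a whole. None of these carries an eligibility limit. The monthly ototoxicity review in 9.5 is not limited to eligible patients either, and crossing the trigger leads to notification and discussion, not an automatic stop. All of this stands. A reader might infer from 9.5 that harms in ineligible patients disappear from the trial's safety results. The documents do not support that; only the planned summary and the trigger comparison lose them.

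A reader might also infer that the restriction always hides harm. Leaving patients out can only lower event counts, but rates and the between-arm difference can move either way, as the last two rows of the table show.

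A third tempting inference is that ineligible patients carry more risk than average. No section reports toxicity in such patients, and Section 3.2 partly closes the organ-function route: a patient whose repeat laboratory values fall outside the limits may not receive protocol therapy. The point does not need this claim.

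It could be said that calling all eligible patients evaluable does not make ineligible patients unevaluable. That reading is weak. Section 9.4 uses the same form of words for response, where 9.3.1 makes eligible patients the denominator, and the trigger sentence names eligible patients outright.

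**Conclusion.** The point holds for two outputs: the toxicity summary for aim 1.2.2 and the hearing-loss comparison. As written, both leave out patients who were dosed and later ruled ineligible, and no other section supplies an all-treated set. The ceiling is 5 of 95 enrolled patients, or 7 of 155 after expansion, and the true number may be lower. The direction of the effect is not predictable. It matters because small counts let one patient decide the trigger near its boundary, and because one missed Grade 5 event on Regimen B would move the upper limit from 6.4% to about 9.5% to 9.7%. These illustrations rest on assumed counts and on 2 or 3 treated ineligible patients on Regimen B. The response analysis and the sample size are unaffected. This is a cheap improvement, not a flaw that threatens the trial.

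**What to change.** In 9.5 and 10.2.1.1, define the toxicity set as all patients who received at least one dose of any protocol agent, grouped by regimen received, whether or not they were later found eligible. In 9.3.4, state that the Grade 3 or higher summary uses this set. In the trigger paragraph of 9.5, use the same set as the population for the hearing-loss comparison, still limited to patients on the interrupted schedule; the threshold and the action that follows stay as they are. Footnote the ineligible patients in the toxicity tables so that readers can see their contribution. Keep the eligible-only set for response in 9.3.1, 9.4 and 10.2.1.2.

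The cost is a few sentences. No new data are needed, because adverse event reporting already carries no eligibility limit, and the target of 90 eligible patients does not change. The downside is that response and toxicity tables will have slightly different denominators: up to 95 for toxicity against 90 for response, or 155 against 148 after expansion.

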10.0 EVALUATION CRITERIA

10.1 Common Terminology Criteria for Adverse Events (CTCAE)

This study will utilize version 5.0 of the CTCAE of the National Cancer Institute (NCI) for toxicity and performance reporting. A copy of the CTCAE version 5.0 can be downloaded from the CTEP website

(http://ctep.cancer.gov/protocolDevelopment/electronic_applications/ctc.htm).

Additionally, toxicities are to be reported on the appropriate case report forms.

Please note: 'CTCAE v5.0' is understood to represent the most current version of CTCAE v5.0 as referenced on the CTEP website (i.e., v5.0 and all subsequent iterations prior to version 6.0).

10.2

Response Criteria for Patients with Solid Tumors

This study will use the revised International Neuroblastoma Response Criteria (INRC) for disease assessment.⁶⁸ The updated response criteria incorporate current approaches to imaging of neuroblastoma, including functional imaging. Furthermore, a standardized approach to assessment of bone marrow involvement is included. The current INRC do **not** include methods of disease assessment that are less sensitive and/or specific for neuroblastoma (⁹⁹Tc bone scan and catecholamine levels).

10.2.1 Definitions

10.2.1.1 Evaluable for toxicity: All eligible patients will be evaluable for toxicity from the time of their first treatment with eflornithine, or irinotecan, temozolomide or dinutuximab.

10.2.1.2 Evaluable for response: All eligible patients will be considered evaluable for response. These patients will have their response classified according to the definitions stated below.

10.2.2 Disease Parameters

10.2.2.1 Measurable disease: Measurable lesions are defined as those that can be accurately measured in at least one dimension (longest diameter to be recorded) as ≥ 20 mm by chest x-ray, as ≥ 10 mm with CT scan, or ≥ 10 mm with calipers by clinical exam. All tumor measurements must be recorded in millimeters (or decimal fractions of centimeters).

Note: Tumor lesions that are situated in a previously irradiated area will be considered measurable if they demonstrate clear evidence of progression after completion of radiation.

10.2.2.2 Malignant lymph nodes: To be considered pathologically enlarged and measurable, a lymph node must be ≥ 15 mm in short axis when assessed by CT scan (CT scan slice thickness recommended to be no greater than 5 mm). At baseline and in follow-up, only the short axis will be measured and followed as per RECIST 1.1 criteria. Patients with neuroblastoma may have conglomerate masses of non-discrete lymph nodes (i.e. multiple contiguous retroperitoneal nodes). When a short axis of a discreet node cannot be identified, a lymph node conglomerate can be measured using the longest diameter of the composite lesion. Tracer avidity of metastatic nodes will be recorded at baseline and during disease evaluations.

10.2.2.3 Non-measurable disease: All other lesions (or sites of disease), including small lesions (longest diameter < 10 mm or pathological lymph nodes with ≥ 10 to < 15 mm short axis), are considered non-measurable disease. Bone lesions, leptomeningeal disease, ascites, pleural/pericardial effusions, lymphangitis cutis/pulmonitis, inflammatory breast disease, and abdominal masses (not followed by CT or MRI), are considered as non-measurable.

Note: Cystic lesions that meet the criteria for radiographically defined simple cysts should not be considered as malignant lesions (neither measurable nor non-measurable) since they are, by definition, simple cysts.

'Cystic lesions' thought to represent cystic metastases can be considered as measurable lesions, if they meet the definition of measurability described above. However, if non-cystic lesions are present in the same patient, these are preferred for selection as target lesions.

10.2.2.4 **Target lesions:** All measurable lesions up to a maximum of 2 lesions per organ and 5 lesions in total, representative of all involved organs, should be identified as **target lesions** and recorded and measured at baseline. Target lesions should be selected on the basis of their size (lesions with the longest diameter), be representative of all involved organs, but in addition should be those that lend themselves to reproducible repeated measurements. It may be the case that, on occasion, the largest lesion does not lend itself to reproducible measurement in which circumstance the next largest lesion which can be measured reproducibly should be selected. For the purposes of response assessment, target lesions are disease sites that are measurable (non-nodal soft tissue mass ≥ 10 mm in longest dimension or lymph node ≥ 15 mm in short axis) and tracer avid OR are biopsy positive for neuroblastoma or ganglioneuroblastoma. The sum of diameters of target lesions is defined as the sum of the short axis of discrete lymph nodes (i.e., cervical, axillary nodes) added to the sum of the longest diameters of non-lymph node soft tissue metastases. The baseline sum diameters will be used as reference to further characterize any objective tumor regression in the measurable dimension of the disease.

10.2.2.5 **Non-target lesions:** All other lesions (or sites of disease) including any measurable lesions over and above the 5 target lesions should be identified as **non-target lesions** and should also be recorded at baseline. Measurements of these lesions are not required, but the presence, absence, or in rare cases unequivocal progression of each should be noted throughout follow-up.

10.2.2.6 **Bone lesions:** Osteomedullary disease will be assessed using ^{123}I -MIBG scans or FDG-PET scans. Technetium bone scans are no longer used as part of the revised INRC and are not included as part of disease reassessments during this trial. The extent of tracer avid disease will be evaluated using the Curie scoring system (see [Appendix IX](#) for worksheet). SPECT may be used to confirm the presence or absence of lesions in a given segment of the body. The absolute Curie score should be reported at baseline. A relative score (Curie score at the time of disease assessment divided by baseline Curie score) should be recorded at the time of each disease evaluation.

10.2.2.7 **Bone marrow disease:** Bilateral bone marrow aspirates and trephine biopsies are required at disease assessment time points (baseline and end of Cycles 2, 4, 6 and every 4th cycle thereafter if bone marrow

involvement at study enrollment or *any* history of bone marrow disease; end of Cycles 2 and 6 for those patients without bone marrow involvement at study enrollment and without *any* history of bone marrow involvement). The extent of marrow involvement in all four samples should be recorded. Use of immunohistochemical staining for evaluation of trephine biopsies is strongly encouraged. The percentage of tumor infiltration of bone marrow space assessed by histologic evaluation of trephine/biopsies or counting the number of tumor cells in aspirates by cytology or immunocytology (recommended if available) divided by the number of hematopoietic/mononuclear cells evaluated to obtain a percentage involvement (methodology described by Burchill et al.).⁷¹ The bone marrow sample with the highest percentage of tumor infiltration is used for response assessment. If > 0% to ≤ 5% tumor infiltration is the highest percentage seen among samples obtained, the result should be recorded as minimal marrow disease.

10.2.3 Response Criteria

PRIMARY (SOFT TISSUE) TUMOR RESPONSE¹

RESPONSE	ANATOMICAL IMAGING + MIBG (FDG-PET²) IMAGING
Complete Response (CR)	
• < 10 mm residual soft tissue at primary site, AND• complete resolution of MIBG or FDG-PET uptake (for MIBG non-avid tumors) at primary site
Partial Response (PR)	
• ≥ 30% decrease in longest diameter (LD) of primary site• MIBG or FDG-PET uptake at primary site stable, improved or resolved
Progressive Disease (PD)	
• > 20% increase in longest diameter taking as reference the smallest sum on study (this includes the baseline sum if that is the smallest on study), AND• a minimum absolute increase of 5 mm in longest dimension³
Stable Disease (SD)	Neither sufficient shrinkage for PR nor sufficient increase for PD at the primary site

¹Not for use in assessment of metastatic sites

² For ¹²³I-MIBG non-avid tumors

³ A mass that has not met PD measurement criteria but has fluctuating ¹²³I-MIBG avidity will not be considered progressive disease.

RESPONSE AT METASTATIC SOFT TISSUE AND BONE SITES⁵

RESPONSE	ANATOMICAL IMAGING + MIBG (FDG-PET ¹) IMAGING
Complete Response (CR)	
 Resolution of all sites of disease defined as: 
 Non-primary target and non-target lesions measure < 10 mm AND Lymph nodes identified as target lesions decrease to a short axis < 15 mm, AND MIBG uptake or FDG-PET uptake (for MIBG non-avid tumors) of non-primary lesions resolves completely
Partial Response (PR)	
 ≥ 30% decrease in sum of diameters² of non-primary target lesions compared to baseline, AND all of the following: 
 Non-target lesions may be stable or smaller in size AND No new lesions AND ≥ 50% reduction in MIBG absolute bone score (Relative MIBG bone score ≥ 0.1 to ≤ 0.5 using as a reference the absolute score for bone lesions from time of enrollment^{4,6}) or ≥ 50% reduction in number of FDG-PET avid bone lesions^{3,4}
Progressive Disease (PD)	Any of the following: 
 Any new soft tissue lesion detected by CT or MRI that is also MIBG avid or FDG-PET avid; Any new soft tissue lesion seen on anatomic imaging that is biopsied and confirmed to be a neuroblastoma or ganglioneuroblastoma; Any new bone site that is MIBG avid and that was not seen on the immediate prior scan; A new bone site that is FDG-PET avid (for MIBG non-avid tumors) AND has CT or MRI findings consistent with tumor OR has been confirmed histologically to be neuroblastoma or ganglioneuroblastoma; > 20% increase in longest diameter taking as reference the smallest sum on study (this includes the baseline sum if that is the smallest on study), AND a minimum absolute increase of 5 mm in sum of diameters of target soft tissue lesions; Relative MIBG score ≥ 1.2 using as reference the lowest absolute score for bone lesions since enrollment^{4,7}
Stable Disease (SD)	Neither sufficient shrinkage for PR nor sufficient increase for PD of non-primary lesions

¹ Used for MIBG non-avid tumors² Sum of diameters is defined as the sum of the short axis of discrete lymph nodes (i.e., cervical, axillary nodes) added to the sum of the longest diameters of non-lymph node soft tissue metastases. Masses of conglomerate non-discrete lymph nodes will be measured using longest diameter.

³ For patients with soft tissue metastatic disease, resolution of MIBG and/or FDG-PET uptake at the soft tissue sites is not required; all size reduction criteria must be fulfilled.

⁴ MIBG-SPECT or MIBG-SPECT/CT may be used for scoring purposes but the same imaging methodology should be used for all evaluations.

⁵ Criteria for soft tissue metastasis not applicable if the patient has only bone metastasis; criteria for bone metastasis not applicable if the patient has only soft tissue metastasis.

⁶ Relative Curie score when assessing patient for partial response: [Current Curie score for bone sites] / [Curie score for bone sites at enrollment].

⁷ Relative Curie score when assessing patient for progressive disease: [Current Curie score for bone sites] / [Lowest Curie score for bone sites since enrollment].

BONE MARROW RESPONSE

RESPONSE	BONE MARROW STATUS ¹
Complete response (CR)	Bone marrow with no tumor infiltration upon reassessment, independent of baseline tumor involvement
Progressive disease (PD)	Any of the following: 
 • Bone marrow without tumor infiltration that becomes > 5% tumor infiltration upon reassessment; or • Bone marrow with tumor infiltration that increases by > 2-fold and has > 20% tumor infiltration upon reassessment.
Minimal disease (MD)	Any of the following: 
 • Bone marrow with \leq 5% tumor infiltration and remains > 0-\leq 5% tumor infiltration upon reassessment; or • Bone marrow with no tumor infiltration that becomes \leq 5% tumor infiltration upon reassessment; or • Bone marrow with >5% tumor infiltration that has > 0-\leq 5% tumor infiltration upon reassessment.
Stable disease (SD)	Bone marrow with tumor infiltration that remains positive with > 5% tumor infiltration upon reassessment but does not meet CR, MD or PD criteria

¹Immunohistochemistry strongly encouraged

DETERMINATION OF OVERALL RESPONSE

In determining overall response, Not Fully Evaluated (NFE) will be used when at least one component of response evaluation was not required and not performed for one or more of the 3 components required for overall response (this will be annotated CR, PR, MR, or SD).

If a component was not performed and was required by protocol, that component will be determined to be Not Done (ND) and the overall response will be Not Done.

RESPONSE	CRITERIA
Complete Response (CR)	All components meet criteria for CR
Partial Response (PR)	PR in at least one component and all other components are either CR, MD (Bone marrow), PR (Soft tissue or Bone) or Not involved (NI); no component with PD.
Minor Response (MR)	PR or CR in at least one component but at least one other component with SD; no component with PD.*
Stable Disease (SD)	SD in one component with no better than SD or NI in any other component; no component with PD.
Progressive Disease (PD)	Any component with PD

NI = Not involved, site not involved at study entry and remains not involved; MD = Minimal Disease, for bone marrow assessment only.

For CR, PR, MR, SD – if one or more component evaluations were not required at that disease evaluation timepoint *AND* they were not performed at the timepoint in question—that response will be annotated as Not Fully Evaluated (NFE).

*Patients who enroll with marrow-only disease who have a marrow response of Minimal Disease will also be coded as having an overall response of Stable Disease.

See [Appendix XIV](#) for additional information regarding overall response assessment

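### The complete-response row for metastatic sites gives two size limits that can both apply to a target lymph node, and the looser one (15 mm) is also the size at which a node becomes a target lesion

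*Combined protocol and SAP*

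**What the plan says.** Section 10.2.2.2 sets the entry size: "a lymph node must be ≥ 15 mm in short axis when assessed by CT scan". Section 10.2.2.4 repeats 15 mm for target lesions and requires that they be measurable "and tracer avid OR are biopsy positive for neuroblastoma or ganglioneuroblastoma". A node can therefore be a target lesion without tracer uptake if a biopsy is positive.

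Section 10.2.2.3 covers smaller lesions. Those under 10 mm, and pathological nodes from 10 to under 15 mm in "short axis), are considered non-measurable disease".

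In Section 10.2.3, CR at metastatic soft tissue and bone sites means that all disease sites have resolved. It has three conditions joined by AND:

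- "Non-primary target and non-target lesions measure < 10 mm";
- "Lymph nodes identified as target lesions decrease to a short axis < 15 mm";
- "MIBG uptake or FDG-PET uptake (for MIBG non-avid tumors) of non-primary lesions resolves completely".

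Partial response (PR) needs a fall of at least 30% in the sum of diameters "of non-primary target lesions compared to baseline". Footnote 3 to that table does not require soft-tissue uptake to resolve for PR. Stable disease (SD) is whatever meets neither the PR nor the progression rule.

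Section 9.3.1 defines a responder as a patient with minor response (MR) or better by the end of 6 cycles on central review. Appendix XIV combines the three components into overall response.

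**The concern.** A metastatic target node is a non-primary target lesion, so on a literal reading the first two conditions of the CR row give it both a 10 mm and a 15 mm limit. If the 15 mm limit governs, two results do not fit the rest of the section. A node can count as resolved at a size that Section 10.2.2.3 still treats as disease. A 12 mm non-target node blocks CR, while a target node that has gone from 16 to 14 mm does not.

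Because 15 mm is also the entry size, a node just above it can cross the limit on a change of a millimetre or two. The metastatic component feeds the primary endpoint, so in some patients such a change would decide responder status.

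**Working it through.** **1. Size arithmetic for a single target node.** Inputs: entry at 15 mm or more, CR size below 15 mm, PR fall of 30%. With baseline b in whole millimetres, reaching 14 mm is a fall of (b − 14)/b. PR needs a fall of 0.30 × b.

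| Baseline (mm) | Fall to 14 mm | Fall needed for PR |
|---|---|---|
| 15 | 1 mm (6.7%) | 4.5 mm |
| 16 | 2 mm (12.5%) | 4.8 mm |
| 18 | 4 mm (22.2%) | 5.4 mm |
| 20 | 6 mm (30.0%) | 6.0 mm |
| 22 | 8 mm (36.4%) | 6.6 mm |

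On a continuous scale the two bars meet where 0.70 × b = 15, so b = 15/0.70 = 21.4 mm. In whole millimetres, CR is the easier size bar only below 20 mm. Two 15 mm nodes that both go to 14 mm take the sum from 30 to 28 mm, a fall of 6.7%, and still meet the nodal size condition.

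**2. When size alone decides.** The tracer condition must already be met. Either the node entered as biopsy-positive and non-avid, so there is no uptake to resolve, or its uptake has already gone. All other metastatic lesions must qualify too. If another component already confers MR or better, responder status does not change.

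**3. Effect on overall response (Appendix XIV; order is primary, metastatic, marrow; NI = not involved).**

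- NI / SD / NI is SD; NI / CR / NI is CR.
- SD / SD / NI is SD; SD / CR / NI is MR.

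In both pairs a non-responder becomes a responder.

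**4. Effect on the primary test.** The plan's figure reproduces. For 40% against 60%, one-sided 0.20 and 80% power, the continuity-corrected pooled test needs 45 per arm, as in Section 9.3.1.1. Approximate power at 45 per arm is Φ[(0.20 − 1/45 − 0.8416 × √(2 × 0.5 × 0.5/45)) / √((0.24 + 0.24)/45)] = 0.806.

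One patient moves an arm's rate by 1/45 = 2.2 points. With 18 control responders, 22 on Regimen B gives p = 0.26 and 23 gives p = 0.199.

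The documents give no frequency of affected patients, so the following is an assumption. If a fraction f of non-responders in both arms is reclassified, the rates become 0.40 + 0.60f and 0.60 + 0.40f, and the difference becomes 0.20 × (1 − f).

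| f | Difference (points) | Approximate power |
|---|---|---|
| 0 | 20.0 | 0.806 |
| 2% | 19.6 | 0.795 |
| 5% | 19.0 | 0.778 |
| 10% | 18.0 | 0.750 |

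**5. With a 10 mm limit.** A 15 mm node must lose more than 5 mm (over 33.3%). The bars would meet at 10/0.70 = 14.3 mm, below the entry size, so nodal CR would always need more shrinkage than PR.

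**The case against.** The strongest objection is that CR is a conjunction. For an avid node, a millimetre or two never gives CR unless uptake has also resolved, and in that case calling the result a false response is hard to defend. On tracer, CR is stricter than PR. A reader might infer that any node of 15 or 16 mm can drift into CR through measurement error, or that CR is generally easier than PR. The documents support neither.

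Second, the size inversion is not peculiar to nodes. A non-nodal target enters at 10 mm and meets its CR size below 10 mm, so the same inversion holds from 10 to 14.3 mm. It comes from pairing an absolute limit with a percentage. This stands, and a change to the nodal limit would not remove it.

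Third, the usual reading is that the specific nodal condition governs target nodes and the general one governs other lesions, since otherwise the nodal condition would be redundant. That largely answers the worry that two central readers would reach different answers, and the documents show no divergent reads. But it settles the matter in favour of 15 mm, so a node that Section 10.2.2.3 still classes as disease counts as resolved. It is true that Section 10.2.2.3 classifies lesions and is not a response rule, but the CR row uses 10 mm for non-target nodes, which matches that class.

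Fourth, the rule is the same in both arms, and the sensitivity of the test to one or two patients is a feature of any binary endpoint at 45 per arm. Both are correct.

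Finally, the cited revised criteria are not available here, so it cannot be said whether the 15 mm line copies them or departs from them.

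**Conclusion.** The point holds in limited form. The CR row gives two size limits that can both apply to a target node. The looser one equals the entry size and conflicts with the document's own class of pathological nodes. A switch from non-responder to responder on 1 to 2 mm is confined to baselines of about 15 to 16 mm, with the tracer condition already met, all other metastatic lesions qualifying and no other component conferring response.

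The size is probably small. The documents do not say how many patients have target nodes in the relevant range, and the power figures rest on an assumed 2% to 10% reclassification of non-responders, equal in both arms. A reader might infer that the primary comparison is unsound; nothing in the documents supports that. This should be fixed because it affects how the primary endpoint is classified and the correction is simple, but it does not undermine the design.

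**What to change.** Reconcile Sections 10.2.2.2 to 10.2.2.4 with the metastatic CR row in Section 10.2.3 so that one size limit applies to target nodes, and check it against the cited revised criteria. The limit that fits the rest of the document is a short axis under 10 mm. It matches the first line of the row, the CR limit for the primary site, and the lower bound of the pathological-node class. If the source supports 15 mm instead, exclude target nodes from the first line explicitly and report the 10 mm version as a sensitivity analysis.

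Apply the settled limit, blind to arm, to every centrally reviewed patient with nodal target lesions, using the recorded measurements or the submitted scans. Report by arm how many responder classifications change.

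The cost is a one-line edit plus the re-derivation, which alters classifications already made and so should be documented as such. A few nodal CRs would become PR or SD. Those that become PR at the metastatic site generally stay responders, so only falls short of 30% lower the response rate, and probably only slightly. The sample size is unaffected. Section 15.2 says that central-review results are not returned to sites, so the re-derivation concerns the endpoint only. Where local response assessments use the same row, the sponsor should reconcile that separately.
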